2.7.1.1 Exposure-Adjusted Incidence Rate

Due to expected differences in exposure and follow-up due to varied duration of study participation between participants, adverse event incidence rates will be provided as “exposure adjusted AE incidence rates”.

The EAIR is defined as the number of subjects with a specific event divided by the total exposure-time among the subjects in the study group. That is, the EAIR is calculated as:

$EAIR = n / \sum t_i$, where n is the number of subjects having the i^{th} type event, and t_i is a subject's exposure time and defined as the shortest of the following:

- 1) time to the first episode of the i^{th} type event (if the event occurs),
- 2) duration of study treatment plus the 16-week washout period (approximately corresponding to five half-lives) after last treatment dose, or
- 3) end of the analysis period (Week 12 for the placebo period, week 36 for all safety follow-up).

The total exposure time of all subjects in a treatment group is $\sum t_i$. The EAIR is interpreted as the number of events occurring in a population per unit time. The exact Poisson 95% confidence interval for the EAIR will be provided as well, where an exact $100*(1-\alpha)\%$ confidence interval will be derived as follows (Garwood 1936, Sahai and Khurshid 1993):

- Lower confidence limit $L = \frac{0.5C_{\alpha/2,2n}}{\sum t_i}$ for $n>0$, 0 otherwise,
- Upper confidence limit $U = \frac{0.5C_{1-\alpha/2,2n+2}}{\sum t_i}$,

where $C_{\alpha,k}$ is the α th quantile of the Chi-square distribution with k degrees of freedom.

Whenever applicable, exposure adjusted incidence rates will be provided for the type as below:

1. TEAE and TESAE: Primary SOC level, PT level
2. Most frequent (at least 5% in any treatment group) TEAE: Primary SOC level, PT level

Treatment emergent AE of special interest.

2.7.1.2 Adverse events of special interest / grouping of AEs

Treatment emergent adverse events of special interest (TEAESIs) for ligelizumab treatment will be summarized in each cohort separately.

AEs of special interest for QGE031 treatment include the following, specified as compound-level risk factors defined in the Case Retrieval Strategy (eCRS). The search criteria in the latest eCRS corresponding the MedDRA version at the database lock will be used and reported in the CSR:

- Hypersensitivity reactions (including anaphylaxis)
- Cardiovascular and Cerebrovascular (CCV) events
- Neoplastic conditions
- Injection site reactions
- Serum Sickness
- Churg-Strauss syndrome-Hypereosinophilic syndrome (HES)
- Parasitic (Helminthic) infections
- Thrombocytopenia

Adjudicated AEs

From the AESIs listed above, the following AEs will be adjudicated by the independent committee. The adjudicated events will be listed and a summary table will be provided following the adjudication.

- Anaphylaxis
- Cardiovascular and Cerebrovascular (CCV) events
- Neoplastic conditions

COVID-19 infection related analyses

Listings of all TEAE COVID infections will be presented. All suspected and confirmed infection will be provided. The COVID-19 infection will be filtered based on eCRS.

2.7.2 Deaths

Death will be reported as part of TESAE with a fatal outcome and will be listed in separate listings.

2.7.3 Laboratory data

The listings for laboratory evaluations will be presented for 3 groups of laboratory tests (hematology, serum chemistry, urinalysis) in each cohort separately.

Listings for the change from baseline to each study visit and maximum/minimum value will be generated. These listings will be presented by test group, laboratory test and treatment group. Change from baseline will only be summarized for subjects with both baseline and post baseline values for quantitative parameters, and the maximum/minimum value could come from post-baseline scheduled, unscheduled or premature discontinuation visits. Data from local laboratories will be presented in the listings together. For point of care tests (POCT), the clinical sites in China will be allowed to analyze several parameters such as urine/serum for pregnancy test and urinalysis as per clinical site practice, these results will be flagged in the listings.

The numerical part of the reported result will be treated as the actual LLOQ or ULOQ. These laboratory values will be displayed in listings using the standard unit with the reported sign (“<” or “>”).

The number of participants with newly occurring or worsening abnormalities during the study will be listed by treatment based on the range of the observed data. A case is considered as a newly occurring abnormality if the value is not notable or missing at baseline but is notable thereafter during the study. A case is considered as a worsening abnormality if the value is notable at baseline and at least one post-baseline value during the study is worse than baseline.

If an adolescent subject turned to be an adult subject during the study, the normal range, notable criteria for analysis will be based on the age by the visit assessment.

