**Table 8-5    Laboratory assessments**

Test Category	Test Name
Hematology	Hemoglobin, Platelets count, Leukocytes, , Differential (Basophils, Eosinophils, Lymphocytes, Monocytes, Neutrophils, ),
Chemistry	Albumin, Alkaline phosphatase (ALP), Alanine aminotransferase (ALT), Aminotransferase (AST), Lactate dehydrogenase (LDH), Calcium, Magnesium, Phosphate, Sodium, Potassium, Creatinine, total bilirubin, Urea Nitrogen or Urea, Uric acid, Glucose (non-fasting)
Urinalysis*	Semi-quantitative “dipstick” evaluation for specific gravity, pH, glucose, protein, bilirubin, ketones, leukocytes and blood will be performed at site. When a dipstick evaluation is abnormal, e.g., positive for White blood cells (WBC) and/or blood, a urine sample must be sent to the Central Lab for microscopic examination including Red blood cells (RBC) and WBC. (Details on collection of urine for analysis by central laboratory are provided to investigators in the Laboratory Manual.)
Coagulation	At screening visit (Visit 1) and Day 1 (Visit 100), coagulation will be assessed by International Normalized Ratio (INR), Activated partial thromboplastin time (APTT)
Parasite screening	Local laboratory assessment of stool samples for parasitic infections ( Section 8.4.4 )
Pregnancy Test*	Serum / Urine pregnancy test ( Section 8.4.3 )

---

\* For point of care tests (POCT), the clinical sites in China will be allowed to analyze several parameters such as urine/serum for pregnancy test and urinalysis as per clinical site practice (refer to China laboratory manual for further details)

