#### **8.4.4 Assessment of parasitic infections**

Reduction in IgE levels may confer increased susceptibility to parasitic helminth infections. The risk of acquiring or activating infections with helminths during or after treatment with anti-IgE therapy such as ligelizumab and omalizumab is suspected to be low. Data from the Phase 2 CQGE031C2201 study in this regard was unremarkable but limited due to the small study sample size.

All participants will be given three stool sample collection kits at screening visit (Visit 1) and Week 32 by the site or site's local laboratory. Participants will take the stool sample kits home and collect stool samples from three different bowel movements, ideally on three different days, within seven days after Visit 1 and in the week prior to Week 36(EOS/PSD). Participants will return the three stool samples to the site or local laboratory as soon as possible after the screening visit (in order to allow processing within the screening period) and at Week 36(EOS/PSD).

Stool samples for parasitic disease will be examined by microscopy for ova and parasites by the local laboratory. The identification of organisms in positive stools will be made by local laboratory. If stool testing is positive for pathogenic helminthic parasites (pathogenic as defined by the local laboratory), the result must be recorded in the source document and the participant will not be randomized and will not be allowed to rescreen. Stool samples negative for pathogenic parasites must be recorded in the source document before Day 1 (Visit 100).

Participants must be advised that if diarrhea, or any other symptoms suggestive of parasitic infection, develops at any time before the end of study, three additional stool samples must be collected at the next visit or sooner and sent to local laboratory for analysis.

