### **11.2 Database management and quality control**

Novartis personnel (or designated CRO) will review the data entered by investigational staff for completeness and accuracy. Electronic data queries stating the nature of the problem and requesting clarification will be created for discrepancies and missing values and sent to the investigational site via the EDC system. Designated investigator site staff are required to respond promptly to queries and to make any necessary changes to the data.

Concomitant treatments and prior medications entered into the database will be coded using the World Health Organization (WHO) Drug Reference List, which employs the Anatomical Therapeutic Chemical classification system. Medical history/current medical conditions and AEs will be coded using the MedDRA terminology.

Laboratory samples will be processed centrally and the results will be sent electronically to Novartis. Stool samples will be processed by local labs and the results will be captured by Novartis via eCRFs.

ECG readings will be processed centrally and results will be sent electronically to Novartis.

[REDACTED] The remaining PROs will be completed by participants on site on the day of applicable visits. [REDACTED]

[REDACTED] The source data collected by the vendor will be sent electronically to Novartis.

At selected sites digital photos will be taken as per [Section 8.5.5](#). These photographs will be sent electronically by the site to the central dermatology-imaging vendor and from there electronically to Novartis.

Dates of screenings, randomizations and screen failures, as well as randomization codes and data about all study treatment (s) dispensed to the participant and all dosage changes will be tracked using IRT. The system will be supplied by a vendor, who will also manage the database. The data will be sent electronically to Novartis (or a designated CRO) at specific timelines.

Each occurrence of a code break via IRT will be reported to the clinical team and monitor. The code break functionality will remain available until study shut down or upon request of Novartis.

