### **Clinical laboratory evaluations**

All laboratory data will be listed by treatment group, participant, and visit/time and if normal ranges are available abnormalities will be flagged.

Descriptive summary statistics for the change from baseline to each study visit will be presented. These descriptive summaries will be presented by laboratory test and treatment group. Change from baseline will only be summarized for participants with both baseline and post baseline values. For categorical parameters, frequencies by categories at each visit will be summarized.

Shift tables using the low/normal/high/ (low and high) classification will be used to compare baseline to the worst on-treatment value.

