2.7.1 Adverse events (AEs)

Treatment emergent adverse events (TEAEs) are events which started on or after the first dose of study treatment and within 16 weeks after the last study treatment, or events present prior to the first dose of study treatment but increased in severity based on preferred term within 16 weeks after the last study treatment.

TEAEs will be summarized in each cohort separately by the actually received treatment group:

- The number and exposure-adjusted incidence of subjects having any TEAE by system organ class (SOC) and preferred term (PT): For the participants in the placebo arm, adverse events after switching to ligelizumab (on or after Week 12) will be summarized separately for the treatment phase. The summary of the TEAEs up to Week 12 will include all the TEAEs up to Week 12 for all the treatment groups, including the placebo only group. The summary of the TEAEs for the entire study will be provided for all the treatment groups listed in Table 2-3.
- The number and exposure-adjusted incidence of subjects having any TEAE by severity: if a subject reported more than one adverse event with the same preferred term, the adverse event with the greatest severity will be presented. If a subject reported more than one adverse event within the same primary system organ class, the subject will be counted only once with the greatest severity at the system organ class level, where applicable.
- The number and exposure-adjusted incidence of subjects having any related TEAEs.: if a subject reported more than one adverse event with the same preferred term, the adverse event with the greatest severity will be presented. If a subject reported more than one adverse event within the same primary system organ class, the subject will be counted only once with the greatest severity at the system organ class level, where applicable.
- The number exposure-adjusted incidence of subjects having any serious treatment emergent adverse events (TESAEs), related TESAEs. The following significant adverse event will be listed - TEAEs leading to discontinuation and dose interruption, and TEAE adverse events of special interest (AESIs). For AESIs with adjudication (anaphylaxis, malignancy, CCV), separate listings will be provided based on the adjudicated results.
- A listing will be provided for safety topics of immunogenicity, COVID-19 infection, Liver Toxicity.

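### SAP 2.7.3 leaves out the stool ova and parasite results that the protocol says it will list, and the Week 36 stool test falls on the last day of the treatment-emergent window

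*SAP*

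**What the plan says.** **Collection.** Protocol 4.5 names parasitic infection as a risk to be monitored. Protocol 8.4.4 and Table 8-1 schedule stool testing at two points only: screening, where a pathogenic helminth excludes the participant, and Week 36/EOS. The Week 36 samples are collected in the preceding week and handed in at the visit. Any other stool test is triggered by symptoms or done at an unplanned visit.

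**Status of the data.** Protocol Table 8-5 places the test among the laboratory assessments: "Local laboratory assessment of stool samples for parasitic infections". Protocol 11.2 adds: "Stool samples will be processed by local labs and the results will be captured by Novartis via eCRFs". For output, protocol 12.5.2 (Clinical laboratory evaluations) says: "All laboratory data will be listed by treatment group, participant, and visit/time and if normal ranges are available abnormalities will be flagged".

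**SAP output.** SAP 2.7.3 says: "The listings for laboratory evaluations will be presented for 3 groups of laboratory tests (hematology, serum chemistry, urinalysis) in each cohort separately". It adds: "Data from local laboratories will be presented in the listings together". No stool listing or table appears elsewhere in the readable SAP, and the readable part of SAP Section 4 does not name this as a change from the protocol.

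**Adverse events.** SAP 2.7.1.2 includes "Parasitic (Helminthic) infections" among the events of special interest. The SAP's outputs for that class cover treatment-emergent events, defined in SAP 2.7.1 as "events which started on or after the first dose of study treatment and within 16 weeks after the last study treatment", or earlier events that worsen in that period.

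**The concern.** The protocol treats the stool result as laboratory data and undertakes to list it. The SAP narrows the laboratory listings to three groups that leave it out, without saying so. Because a positive screen excludes, a positive stool at Week 36 comes after a negative screen, and it is the only scheduled evidence on silent helminth infection after dosing.

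Without a stool listing, reporting depends on the adverse-event route, which has two weak points. First, under protocol 10.1.1 a test result becomes an adverse event only if it causes signs or symptoms, is judged clinically significant or needs therapy, so a silent positive depends on the investigator's judgement. Second, the Week 36 visit sits on the edge of the treatment-emergent window, and the documents do not say whether an infection found by stool test starts at sample collection or at the laboratory report. At stake is whether a positive result already in the database appears in any SAP output.

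**Working it through.** **Inputs.** Study days from protocol Table 8-1: Week 16 = Day 113, Week 20 (last planned dose) = Day 141, Week 24 = Day 169, Week 36 = Day 253. Treatment-emergent window from SAP 2.7.1: 16 weeks = 16 × 7 = 112 days after the last dose. Stool collection from protocol 8.4.4: the week before Week 36, about Day 246 to Day 253.

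**Step 1, the protocol's own interval.** Protocol 3.1 places Week 36 at 16 weeks after the last dose. 253 − 141 = 112 days, and 112 / 7 = 16.0 weeks. This is reproduced. The margin against the window is 112 − 112 = 0 days.

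**Step 2, where a Week 36 finding falls.** Days after last dose = onset date − last dose date.

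| Date used as onset | Days after last dose | In window? |
|---|---|---|
| Collection, all doses taken, visit on Day 253 | 246 − 141 = 105 to 253 − 141 = 112 | Yes |
| Laboratory report 1 to 14 days after the visit | 112 + 1 = 113 to 112 + 14 = 126 | No |
| Collection, visit *k* days late | 105 + *k* to 112 + *k* | Partly for *k* = 1 to 7; no for *k* ≥ 8 |
| Collection, Week 20 dose missed, visits on schedule | 246 − 113 = 133 to 253 − 113 = 140 | No |

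The documents give no laboratory turnaround. The range of 1 to 14 days is an assumption, and any report after Day 253 gives the same answer.

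**Step 3, early discontinuation.** Protocol 9.1.1 puts the end-of-treatment assessments 4 weeks (28 days) after the last dose, followed by the Week 28 to 36 visits. If these are spaced from that visit as in Table 8-1, the final visit is 28 + (253 − 169) = 28 + 84 = 112 days after the last dose, the same boundary. This is relevant because SAP 1.1.2 moved everyone still on treatment into follow-up.

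**Step 4, symptom-triggered testing.** Table 8-1 limits additional parasite assessments to symptoms arising before the last dose. Section 8.4.4 extends them to the end of the study. The two passages disagree. On the Table 8-1 reading, Week 36 is the only planned stool check after the last dose.

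**The case against.** A strong defence can be made, and much of it stands.

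- **The protocol does plan an output.** Its rule to list all laboratory data, read with Table 8-5, covers stool. The gap is therefore between protocol and SAP. This stands.
- **The SAP's local-laboratory sentence might cover stool.** It sits inside listings already confined to three groups and adds no fourth, so it does not fill the gap.
- **A positive result can reach the adverse-event page.** Protocol 8.4.1 and 10.1.1 require this if the result is clinically significant or needs therapy, and an in-window helminth infection is then reported as an event of special interest. This stands, but the route depends on judgement.
- **Loss from the window needs particular circumstances.** No document tells a site to enter the report date as onset. The imputation rules in SAP 5.3.2 generally move an incomplete start date earlier. This stands, although no document prescribes the collection date either.
- **An out-of-window adverse event is not invisible.** Protocol 12.5.2 displays all adverse-event information, not only treatment-emergent events. This stands for the protocol. The SAP's outputs for this class are treatment-emergent only.
- **Hidden text.** Protocol 'Other safety evaluations' is blacked out, and material after SAP 2.7.4.2 is not shown. A stool output there cannot be excluded.
- **The trial was stopped.** SAP 1.1 and 1.1.2 report 39 enrolled and only 3 who had completed Week 12, so full completers are few or none. This limits the size but does not remove the point: the SAP keeps safety listings, and Step 3 gives early stoppers the same boundary.

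A reader might infer that every silent infection found at Week 36 will go unreported. The documents do not support that: dated by collection in a full completer with an on-time visit, an infection recorded as an adverse event is counted.

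**Conclusion.** The point holds as an undeclared omission in the readable SAP. A laboratory result that the protocol collects, classifies and says it will list has no place in SAP 2.7.3. It is the only scheduled post-dose check for a named event of special interest. This part does not depend on how events are dated.

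The window problem is real but conditional. The margin is 0 days, and a Week 36 finding falls outside the SAP's treatment-emergent outputs if it is dated by a later report, if the visit is late enough, or if the Week 20 dose was missed (133 to 140 days even by collection date). It rests on the Table 8-1 schedule and on the documents' silence about the onset date. The number of participants affected cannot be stated, and in the stopped trial it is at most small.

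A reader might also infer that every helminth-positive post-baseline stool should count as a treatment-emergent event of special interest. The documents do not support that either. It would bypass the adverse-event criteria in protocol 10.1.1, the search definition in SAP 2.7.1.2 and the 16-week window.

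**What to change.** 1. In SAP 2.7.3, add a by-participant listing of stool ova and parasite results at screening, unscheduled visits and Week 36/EOS, with the organism, and a count by treatment group. Present both regardless of the treatment-emergent window. If the omission is deliberate, declare it and give the reason in SAP Section 4.
2. In SAP 2.7.1, state that when a parasitic infection adverse event rests on a stool result, its onset is the date of sample collection. Leave the adverse-event criteria, the event search definition and the 16-week window as they are.
3. Reconcile protocol Table 8-1 with Section 8.4.4 on how long symptom-triggered stool testing applies.

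The cost of the first two is a few lines of SAP wording, one listing and one count from data already captured in the eCRF, for 39 enrolled participants. The third is a wording clarification in the protocol.

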2.7.4 Other safety data

2.7.4.1 ECG and cardiac imaging data

All listings will be provided for each CINDU cohort separately. A listing of all newly occurring or worsening abnormalities will be provided, as well as a by-subject listing of all quantitative ECG parameters.

The following will be considered as notable values for adults: QT > 500 msec; QTcF > 450 msec (males), QTcF > 460 msec (females); QTcF change from baseline > 30 msec, >60 msec; PR > 250 msec. The following were considered as notable ECG values for adolescents: QTcF >450 msec (males), QTcF >460 msec (females); QTcF change from baseline >30 msec, >60 msec; PR >250 msec.

[figure not shown]
2.7.4.2 Vital signs

[figure not shown]
Subjects with notable vital signs as defined below will be listed.

[figure not shown]
For adults:

[figure not shown]
- Hypertension (systolic blood pressure of ≥ 140 mmHg and/or diastolic blood pressure of ≥ 90 mmHg) or hypotension (systolic blood pressure of < 90 mmHg and/or diastolic blood pressure of < 60 mmHg).
- Pulse rate below 60 bpm (bradycardia) or above 100 bpm (tachycardia).

[figure not shown]
For adolescents: same normal range for adult will be used for adolescents.

[figure not shown]

[figure not shown]

[figure not shown]

[figure not shown]

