## 16 Appendices

### 16.1 Appendix 1: Clinically notable laboratory values and vital signs

The following other specific criteria have been identified for this study:

Platelets < 75 000/ $\mu$ L

· Any patient who have platelets < 75 000/ $\mu$ L after being randomized should discontinue study treatment.

For all other laboratory assessments, the Central Laboratory will flag laboratory values falling outside of the normal ranges on the Central Laboratory Report (which the investigator should review and sign-off) and the investigator will report any values considered clinically significant in the eCRF.

Notable values for vital signs and change from baseline will be summarized.

Notable values for adults are defined as follows:

- heart rate of < 60 and > 100 bpm
- systolic blood pressure of < 90 and  $\geq$  140 mmHg
- diastolic blood pressure of < 60 and  $\geq$  90 mmHg

For ECGs a notable QTc value is defined as a QTcF interval of greater than 450 ms for males or greater than 460 ms for females - all such ECGs will be flagged by the Central CRO's cardiologist and require assessment for clinical relevance by the investigator. For adolescent participants, the Central CRO will use age-and gender-specific reference values.

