Appendix 1.1: Clinically notable vital signs - adolescent participants

Guideline for pediatric blood pressure measurements:

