The blood pressure values in the table above were adapted from [Flynn et al 2017](#) by modifying 5% of height (in table 6 of the publication) with 50% height to represent 'average' child height per age/sex. The normal values for vital signs in children vary greatly with age, growth and development. Selected BP threshold values serve as a representative guide of 'elevated BP' for a child of 'average' size.

The purpose of the values listed in this table is to guide investigators to identify or screen for values of concern in pediatric participants by age. The significance of these findings must be considered in view of the participant's disease, time course and overall clinical condition.

 Flynn JT, Kaelber DC, Baker-Smith CM, et al. Clinical practice guideline for screening and management of high blood pressure in children and adolescents

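### The SAP's notable vital-sign listing applies adult limits to adolescents, while protocol Appendix 1 gives them separate values by age and sex; a band of systolic and pulse values goes unflagged

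*SAP*

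**What the plan says.** **Protocol.** Table 8-4 refers to Appendix 1 for the definition of clinically notable vital signs. Appendix 1 gives limits expressly for adults: heart rate below 60 or above 100 bpm, systolic pressure below 90 or at least 140 mmHg, diastolic pressure below 60 or at least 90 mmHg. It also says that notable values will be summarized. A separate part, Appendix 1.1, is headed "Clinically notable vital signs - adolescent participants" and contains Table 16-2, with values for each year of age from 12 to 17. The note to that table says its purpose is to "guide investigators to identify or screen for values of concern in pediatric participants by age". In Section 12.5.2 the protocol plans to list all vital signs, to flag abnormalities where ranges exist, and to summarize adults and adolescents separately.

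**SAP.** Section 2.7.4.2 says "Subjects with notable vital signs as defined below will be listed". For adults, high blood pressure is "systolic blood pressure of ≥ 140 mmHg and/or diastolic blood pressure of ≥ 90 mmHg", and pulse is notable below 60 or above 100 bpm. For adolescents the "same normal range for adult will be used for adolescents".

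**ECG.** Protocol Section 12.5.2 and Appendix 1 both say "For adolescent participants, the Central CRO will use age-and gender-specific reference values". SAP 2.7.4.1 has a sentence beginning "The following were considered as notable ECG values for adolescents" and gives the same QTcF, QTcF-change and PR limits as for adults.

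**The concern.** The protocol separates adolescents from adults when it defines a notable vital sign, and the SAP merges them without giving a reason. The visible SAP text lists only participants who are notable under its own rule, so the choice of limit decides whether an adolescent appears in that listing.

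Early termination does not explain the choice, because a shortened study can still use an age table. SAP 2.7.3 also says that laboratory normal ranges and notable criteria follow the participant's age at the visit, so the SAP accepts elsewhere that criteria can differ between adolescents and adults. With efficacy testing and efficacy summary tables dropped, safety output is much of what the study will report.

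**Working it through.** No power or error-rate calculation applies. The check compares the two sets of limits and counts the values that pass one but not the other.

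**Systolic pressure.** Inputs are the Table 16-2 figures (notable if above the figure) and the SAP limit (notable if 140 mmHg or more). In whole mmHg, the unlisted band runs from figure + 1 to 139, which is 139 − figure values.

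| Age | Boys: figure | Unlisted | Count | Girls: figure | Unlisted | Count |
|---|---|---|---|---|---|---|
| 12 | 117 | 118–139 | 22 | 118 | 119–139 | 21 |
| 13 | 121 | 122–139 | 18 | 121 | 122–139 | 18 |
| 14 | 126 | 127–139 | 13 | 122 | 123–139 | 17 |
| 15 | 128 | 129–139 | 11 | 122 | 123–139 | 17 |
| 16 | 129 | 130–139 | 10 | 123 | 124–139 | 16 |
| 17 | 131 | 132–139 | 8 | 124 | 125–139 | 15 |

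The limits themselves differ by 140 − 131 = 9 to 140 − 117 = 23 mmHg in boys, and by 140 − 124 = 16 to 140 − 118 = 22 mmHg in girls.

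**Pulse.** Table 16-2 prints two ranges, 62–96 and 60–92 bpm, which I take to cover ages 12–14 and 15–17. Against the SAP limits of below 60 or above 100, the unlisted values are 60–61 and 97–100 bpm at ages 12–14, and 93–100 bpm at ages 15–17.

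**Diastolic pressure.** Table 16-2 prints this column with a less-than sign (below 75 to below 81, by age and sex), while its note describes the blood pressure values as a guide to elevated pressure. The direction is therefore unclear:
- Read as upper limits, unlisted values start at 76 to 82 mmHg, by age and sex, and run to 89.
- Read as printed, they run from 60 up to 74 to 80 mmHg.

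The conclusion does not rest on this column.

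**ECG.** The protocol gives no adolescent figures, so no band can be computed. SAP 2.7.4.1 also provides a by-subject listing of every quantitative ECG parameter.

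**The case against.** **Table 16-2 is guidance.** Its title and note present it as a screening aid for investigators, for a child of average size, to be weighed against the clinical picture. No sentence says that it drives the statistical listing. This is fair and lowers the weight of the point. It does not remove the conflict: the table stands under the adolescent heading for notable vital signs, Table 8-4 points to Appendix 1 for the definition, and the limits the SAP borrows are labelled there as adult.

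**Raised adolescent blood pressure would go unreported.** A reader might infer this, but the documents do not support it. An adolescent at or above 140 mmHg systolic or 90 mmHg diastolic is listed under the SAP rule, and one within the band is listed if another vital sign qualifies. The protocol planned a full vital-sign listing, and the SAP section has gaps where content was not reproduced, so omission from all output is not shown. Investigator review and adverse event recording at the site are unaffected.

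**The SAP's low limits are also wrong for adolescents.** This too is tempting. Table 16-2 gives no lower systolic figure, and its diastolic column has no settled direction, so there is no clear protocol limit to contradict.

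**The ECG rule is an equal contradiction.** It is weaker. The protocol assigns the age- and gender-specific references to the Central CRO's reading, which can coexist with separate SAP flags. Exclusion criterion 24 uses 450 and 460 ms without regard to age, and the SAP's adolescent set omits the adult QT limit of 500 ms. Only flagging is in question; no ECG value is lost.

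**The departure may be recorded.** Some items in the SAP's lists of changes are redacted, so only the visible entries can be checked.

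**Conclusion.** The conflict is real and narrow. Under SAP 2.7.4.2 as written, adolescent systolic values above the Table 16-2 figure and below 140 mmHg (8 to 22 whole-number values in boys, 15 to 21 in girls) and pulse values above 96 or 92 up to 100 bpm do not by themselves bring a participant into the notable vital-sign listing.

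This assumes that readings are taken in whole mmHg and bpm, that the two printed heart-rate ranges cover ages 12–14 and 15–17, and that Table 16-2 is the protocol's adolescent definition of notable.

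The practical effect is small. The SAP reports 39 participants enrolled and 3 with a completed Week 12 visit. Protocol Section 5 expected few adolescents and set no minimum. Their number is not given and could be zero. Efficacy and adverse event outputs are untouched.

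**What to change.** Reconcile SAP 2.7.4.2 with protocol Appendix 1.1 in one of two ways:
- flag adolescents against the protocol's own adolescent values, after the printed direction of the diastolic column in Table 16-2 has been reconciled with its note; or
- keep the single range, and record and justify the departure in SAP Section 4.

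As a secondary item, add a sentence to SAP 2.7.4.1 saying how its adolescent ECG flags relate to the Central CRO's age- and gender-specific references.

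The cost is a lookup by age and sex in one listing program and a few lines of SAP text. No new data are needed.
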